5.6.1.2.1 BP arm

- Participants on the BP will be asked about their glucose control and study staff will educate as needed. The study staff may suggest a change to the permanent glucose target if indicated.

5.6.1.2.2 UC arm

- No modifications will be made to dosing regimens for participants in the usual care arm.
- Study staff will confirm the participant is wearing the study CGM, and answer any questions the participant may have about the CGM. They will remind the participant to replace the study CGM after 10 days.

5.6.1.3 Crossover Visit (Visit 5):

- At the end of the first study period (Day 14 [+2]), participants will return to the clinic and answer the post questionnaires for the study arm.
- A urine pregnancy test will be performed in participants of child-bearing potential. If the test is positive, the participant will be informed of the result and the next planned study arm will not proceed. The date of the last menstrual period will also be documented.
- Any changes to medications or medical history and any adverse events that may have occurred since the last study visit will be documented.

- All study devices applicable to the arm just completed will be downloaded
 - BP arm: iLet and study glucometer and ketone meter
 - UC arm: Dexcom G6 and study glucometer
- Participants will repeat psychosocial questionnaires (including quality of life, fear of hypoglycemia, diabetes distress).
 - Participants coming off of the BP arm will be asked to complete the Bionic Pancreas User Opinion Survey
- Participants will then start over with Day 1 procedures for the arm they are randomized to next. This may occur immediately, or within 14 days after the completion of the first arm.
 - If the participant is switching from usual care to bionic pancreas:
 - If using an insulin pump (EN group), their own insulin infusion pump will be stopped and disconnected if applicable, and its infusion set will be removed
 - If using MDI therapy (PC group), they will be instructed not to take any additional insulin injections once the bionic pancreas is started, unless instructed to do so by study staff
 - If the participant is switching from bionic pancreas to usual care, a provider (MD or NP) will review the last several hours of insulin dosing and assist the participant in resuming their usual care.
 - For participants whose usual care is MDI therapy:
 - If normal long-acting dose time is MORNING:
 - Morning study visit – take full dose at visit, take next day dose at usual time
 - Afternoon study visit – three quarters of normal dose at visit, take next day dose at usual time
 - If normal long-acting dose time is EVENING:
 - Morning study visit – take half of full dose at visit (acts as loading dose), take full dose at normal time that same evening
 - Afternoon study visit – take one fourth of full dose at visit (acts as loading dose), take full dose at normal time that same evening
 - Investigators may use a different approach according to their judgment.

5.6.1.4 Final Visit (Visit 8):

- Any changes to medications or medical history and any adverse events that may have occurred since the last study visit will be documented.
- The Dexcom CGM sensor and all bionic pancreas infusion sites will be removed, as necessary.
- All study devices, including the iLet, Dexcom G6, and the study glucose and ketone meters will be downloaded.
- If the participant is coming off of the bionic pancreas, a provider (MD or NP) will review the last several hours of insulin dosing and assist the participant in resuming their usual care.
 - For participants whose usual care is MDI therapy:
 - If normal long-acting dose time is MORNING:
 - Morning study visit – take full dose at visit, take next day dose at usual time
 - Afternoon study visit – three quarters of normal dose at visit, take next day dose at usual time

- If normal long-acting dose time is EVENING:
 - Morning study visit – take half of full dose at visit (acts as loading dose), take full dose at normal time that same evening
 - Afternoon study visit – take one fourth of full dose at visit (acts as loading dose), take full dose at normal time that same evening
 - Investigators may use a different approach according to their judgment.
- Participants will be explicitly instructed to resume their usual, pre-study glucose monitoring and to contact their usual diabetes care provider in case any questions or concerns arise about their usual diabetes care following completion of the study.
- All collected equipment will be cleaned using the validated cleaning and disinfecting procedures.
- Participants will be reminded to bring their own pump (EN group) or MDI supplies (PC group), and all other appropriate supplies and insulin to this visit.
- Participants will repeat psychosocial questionnaires (including quality of life, fear of hypoglycemia, diabetes distress).
 - Participants coming off of the BP arm will be asked to complete the Bionic Pancreas User Opinion Survey

5.6.2 *Visit Procedures for telehealth visits*

- Supplies will be shipped to the participant in advance of the scheduled study start visit (Day 1 Visit immediately below). They will be instructed not to unpack any study materials until the scheduled telehealth visit. This will include a scale for measurement of weight, a home pregnancy testing kit, and supplies required for the study.
- All TH study visits will be completed using HIPAA compliant videoconferencing software.

5.6.2.1 Day 1 Visit (Visit 2):

- The body weight of the participant will be verbally self-reported by the participants, who will be instructed to use the scale provided.
- A urine pregnancy test in participants of child-bearing potential will be completed at home using the study-provided pregnancy test at the start of the first arm. Participants will be instructed to complete the pregnancy test during the virtual visit and to show result to study staff. If the test is positive, the participant will be informed of the result and the visit will be ended. The date of the last menstrual period will also be documented.
- Study staff will review any changes in the participant's medical history or medications to ensure continued eligibility, and any adverse events that may have occurred since their screening visit.

5.6.2.1.1 *Participants randomized to usual care:*

- Study staff will review supplies provided and the study procedures.
- Participants will be trained how to insert, maintain and use the Dexcom G6.
- The participants will wear a Dexcom G6 sensor and study staff will confirm they are doing it properly.

5.6.2.1.2 *Participants randomized to bionic pancreas:*

- Study staff will review supplies provided and the study procedures.
- Participants will be trained how to insert, maintain and use the Dexcom G6 CGM.
- The participants will wear a Dexcom G6 sensor and study staff will confirm they are doing it properly.
- Participants will be trained to use the iLet, including navigating the GUI, filling and installing

cartridges and inserting infusion sets.

- Participants will set up the iLet and insert the infusion set and study staff will confirm they are doing it properly.
- The control algorithm will be initialized with the participant's weight.
- If using an insulin pump (EN group), their own insulin infusion pump will be stopped and disconnected if applicable, and its infusion set will be removed.
- If using MDI therapy (PC group), they will be instructed not to take any basal insulin starting the morning of this study visit, and no additional insulin injections once the bionic pancreas is started, unless instructed to do so by study staff
 - Participants on multiple daily injections (MDI) may be started on the iLet without a need for adjustment of their long-acting insulin dose. The new equilibrium will not be reached until all the long-acting insulin has completely cleared their system, which may take 48 hours or more. Participants must be advised that they may see escalating dosing by the iLet during this period.
 - Investigators may consider starting MDI users at the "higher" glucose target setting. If the "higher" setting is used, wait ~2 days before moving down to the default target.
- Participants will complete Clarke's Instrument for Impaired Awareness of Hypoglycemia.
 - Participants with a score > 4 will be instructed to check BG at 2am for the first 2 nights using the iLet

5.6.2.2 Mid-period Follow Ups (Visits 3, 4, 6, and 7):

- Participants may complete a virtually supervised site change, as needed or requested based on participant's prior experience and comfort level.
- All participants will have a virtual phone visit on Day 2 and Day 5 (+/- 2 days) to assess device adaptation, glucose control, and to answer any questions the participant may have.
- Study staff will query the participant for any adverse events and assess the participant's ability to follow protocol and, if applicable, use the device at this time.

5.6.2.2.1 *BP arm:*

- Participants on the BP will be asked about their glucose control and study staff will educate as needed. The study staff may suggest a change to the permanent glucose target if indicated.

5.6.2.2.2 *UC arm*

- No modifications will be made to dosing regimens for participants in the usual care arm.
- Study staff will confirm the participant is wearing the study CGM, and answer any questions the participant may have about the study CGM. They will remind the participant to replace the study CGM after 10 days.

5.6.2.3 Crossover Visits (Visit 5):

- At the end of the first study period (Day 14 [+2]), participants will have a virtual study visit and answer the post questionnaires for the study arm.
- Study staff will review any changes in the participant's medical history or medications to ensure continued eligibility, and any adverse events that may have occurred since their screening visit.
- A urine pregnancy test will be performed in participants of child-bearing potential. Participants will be instructed to complete the pregnancy test during the virtual visit and to show result to study staff. If the test is positive, the participant will be informed of the result and the next planned study arm will not proceed. The date of the last menstrual period will also be

documented.

- They will start over with Day 1 procedures for the arm they are randomized to next. This may occur on the same day, or within 14 days of the final visit of the first arm.
 - If the participant is switching from usual care to bionic pancreas:
 - If using an insulin pump (EN group), their own insulin infusion pump will be stopped and disconnected if applicable, and its infusion set will be removed.
 - If using MDI therapy (PC group), they will be instructed not to take any basal insulin starting the morning of this study visit, and no additional insulin injections once the bionic pancreas is started, unless instructed to do so by study staff
 - If the participant is switching from bionic pancreas to usual care, a provider (MD or NP) will review the last several hours of insulin dosing and assist the participant in resuming their usual care.
 - For participants whose usual care is MDI therapy:
 - If normal long-acting dose time is MORNING:
 - Morning study visit – take full dose at visit, take next day dose at usual time
 - Afternoon study visit – three quarters of normal dose at visit, take next day dose at usual time
 - If normal long-acting dose time is EVENING:
 - Morning study visit – take half of full dose at visit (acts as loading dose), take full dose at normal time that same evening
 - Afternoon study visit – take one fourth of full dose at visit (acts as loading dose), take full dose at normal time that same evening
- Investigators may use a different approach according to their judgment.
- Participants will repeat psychosocial questionnaires (including quality of life, fear of hypoglycemia, diabetes distress).
 - Participants coming off of the BP arm will be asked to complete the Bionic Pancreas User Opinion Survey

5.6.2.4 Final Visit (Visit 8):

- The body weight of the participant will be documented using the scale provided.
- Any changes to medications or medical history and any adverse events that may have occurred since the last study visit will be documented.
- The Dexcom CGM sensor and all bionic pancreas infusion sites will be removed, as necessary.
- Participants will be reminded to have available their own pump (EN group) or MDI supplies (PC group), and all other appropriate supplies and insulin at this visit.
- If the participant is coming off of the bionic pancreas, a provider (MD or NP) will review the last several hours of insulin dosing and assist the participant in resuming their usual care.
 - For participants whose usual care is MDI therapy:
 - If normal long-acting dose time is MORNING:
 - Morning study visit – take full dose at visit, take next day dose at usual time
 - Afternoon study visit – three quarters of normal dose at visit, take next day dose at usual time
 - If normal long-acting dose time is EVENING:
 - Morning study visit – take half of full dose at visit (acts as loading

- dose), take full dose at normal time that same evening
- Afternoon study visit – take one fourth of full dose at visit (acts as loading dose), take full dose at normal time that same evening
 - Investigators may use a different approach according to their judgment.
- Participants will be explicitly instructed to resume their usual, pre-study glucose monitoring and to contact their usual diabetes care provider in case any questions or concerns arise about their usual diabetes care following completion of the study.
- All study devices, including the iLet, Dexcom G6, and the study glucose and ketone meters will be packaged by participants into supplied packing and shipping materials, and returned to the study site using supplied prepaid shipping label/box.
 - Upon receipt of the materials at the site, equipment will be cleaned and disinfected by the study team using validated procedures.
 - The iLet, Dexcom G6, and study glucose and ketone meters will be downloaded.
- Participants will repeat psychosocial questionnaires (including quality of life, fear of hypoglycemia, diabetes distress).
 - Participants coming off of the BP arm will be asked to complete the Bionic Pancreas User Opinion Survey

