5.1 Study Design

This study will assess delivery of the insulin-only iLet bionic pancreas by primary care providers and endocrinologists, as well as delivery of the iLet bionic pancreas via in-person training and support vs telehealth training and support. It will employ a two-center, random-order, two-arm cross-over trial design in a home-use setting in 40 adult participants (18-85 years of age) with type 1 diabetes. This number is based on 10 participants per arm, per site, which has been successfully implemented in previous iLet studies and which has yielded highly significant results in those studies. The two centers will be community-based primary care and academic medical center-based endocrinology. Study participants will be managed by appropriate site-specific study team clinicians: endocrinology providers at MGH, or primary care providers at CU.

The two 14-day study arms will occur in a random-order cross-over design. One arm will involve using the insulin-only iLet bionic pancreas and the other arm will involve insulin delivery via the participants' usual care (multiple daily injections or insulin pump, depending on the study site). Half of the participants will receive care via in-person visits, and the other half will receive care exclusively via telehealth visits. This will result in four study cohorts overall [endocrinology in-person (EN-IP), endocrinology telehealth (EN-TH), primary care in-person (PC-IP), primary care telehealth (PC-TH)].

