5.5.3 Randomization of Study Arm Sequence

Participants will be recruited specifically into the in-person or telehealth cohorts, based on their circumstances. Once the participant has been enrolled and eligibility has been established, participants within each of these cohorts will be randomized to one of two possible study arm sequences.

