5.6 Study Visit Procedures

5.6.1 Visit Procedures for in-person (IP) visits

5.6.1.1 Day 1 Visit (Visit 2):

- The body weight of the participant will be documented.
- A urine pregnancy test will be performed in participants of child-bearing potential at the start of the first arm. If the test is positive, the participant will be informed of the result and the visit will be ended. The date of the last menstrual period will also be documented.
- Study staff will review any changes in the participant's medical history or medications to ensure continued eligibility, and any adverse events that may have occurred since their screening visit.

5.6.1.1.1 Participants randomized to usual care:

- Study staff will provide supplies and review the study procedures.
- Participants will be trained how to insert, maintain and use the Dexcom G6 (in blinded mode if they are not a CGM user).
- The participants will wear a Dexcom G6 sensor and study staff will confirm they are doing it properly.

5.6.1.1.2 Participants randomized to bionic pancreas:

- Study staff will provide supplies and review the study procedures.
- Participants will be trained how to insert, maintain and use the Dexcom G6 CGM.
- The participants will wear a Dexcom G6 sensor and study staff will confirm they are doing it

properly.

- Participants will be trained to use the iLet, including navigating the GUI, filling and installing cartridges and inserting infusion sets.
- Participants will set up the iLet and insert the infusion set and study staff will confirm they are doing it properly.
- The control algorithm will be initialized with the participant's weight.
- If using an insulin pump (EN group), their own insulin infusion pump will be stopped and disconnected if applicable, and its infusion set will be removed
- If using MDI therapy (PC group), they will be instructed not to take any additional insulin injections once the bionic pancreas is started, unless instructed to do so by study staff
 - Participants on multiple daily injections (MDI) may be started on the iLet without a need for adjustment of their long-acting insulin dose. The new equilibrium will not be reached until all the long-acting insulin has completely cleared their system, which may take 48 hours or more. Participants must be advised that they may see escalating dosing by the iLet during this period.

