 - Investigators may consider starting MDI users at the "higher" glucose target setting. If the "higher" setting is used, wait ~2 days before moving down to the default target.
- Participants will complete Clarke's Instrument for Impaired Awareness of Hypoglycemia.
 - Participants with a score > 4 will be instructed to check BG at 2am for the first 2 nights using the iLet

5.6.1.2 Mid-period Follow Ups (Visits 3, 4, 6, and 7):

- Study staff may supervise the first site change via a video visit, as needed or requested based on participant's prior experience and comfort level
- All participants will have a virtual phone visit on Day 2 and Day 5 (+/-2 days) to assess device adaptation, glucose control, and to answer any questions the participant may have
- Study staff will query the participant for any adverse events and assess the participant's ability to follow protocol and, if applicable, use the device at this time.

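### The last scheduled adverse-event query is Visit 8, the visit at which usual care-then-iLet participants come off the iLet, so scheduled safety follow-up of switch-off depends on randomised sequence

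*Combined protocol and SAP*

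**What the plan says.** The Schedule of Visit Procedures marks S/AE querying at Visits 2 to 8. Visit 8 is the last column.

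The final visit is set out in 5.6.1.4 (in person) and 5.6.2.4 (telehealth), in near-identical terms:
- The AE query looks backward: "Any changes to medications or medical history and any adverse events that may have occurred since the last study visit will be documented".
- Study glucose recording stops at the same visit: "The Dexcom CGM sensor and all bionic pancreas infusion sites will be removed, as necessary". Study devices are downloaded, or shipped back in the telehealth groups.
- A provider helps anyone coming off the iLet to resume usual care. For injection users the protocol gives its own resumption schedule, part of which runs past the visit. One branch reads "Morning study visit – take half of full dose at visit (acts as loading dose), take full dose at normal time that same evening". Investigators may depart from it.
- Later concerns go elsewhere: "Participants will be explicitly instructed to resume their usual, pre-study glucose monitoring and to contact their usual diabetes care provider" if questions or concerns about their usual diabetes care arise after the study.

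Participants who have the iLet first come off it at Visit 5 and then start the usual care arm, at once or within 14 days. The Day 1 procedures include an AE review. After that, 5.6.1.2 and 5.6.2.2 state "All participants will have a virtual phone visit on Day 2 and Day 5", with an AE query by study staff. Section 5.7 requires a daily survey in all study arms, and the study CGM is worn in the usual care arm.

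On sequence, 5.5.3 says "participants within each of these cohorts will be randomized to one of two possible study arm sequences" and gives no ratio. Section 6.7.1 defines when a treatment-emergent AE can begin but not when collection stops.

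**The concern.** Taking a participant off the iLet is a study procedure carried out by study providers. For injection users it follows a protocol-specified schedule. In one sequence it is followed by scheduled AE queries, and in the other it coincides with the last one. A query about events since the previous visit cannot pick up an event that follows a switch made at that same visit.

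The safety endpoints in 6.4 are the frequencies of AEs, severe hypoglycemia and DKA. The trial's title includes safety of deployment by primary care and by telehealth, and returning pump-naïve injection users to injections is part of that experience. As planned, the safety summary would rest on systematic follow-up of this step in only about half of participants, and the half is determined by randomisation. Events that are never asked about cannot be recovered by later analysis.

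**Working it through.** The plan gives no figure on this point, and 6.6 says no formal sample size calculation was done, so there is nothing to reproduce.

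**Step 1. Scheduled observation after switch-off, by sequence**

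| | iLet, then usual care | Usual care, then iLet |
|---|---|---|
| Switch-off visit | Visit 5 | Visit 8 |
| Next scheduled AE query | Start of next arm (same day to 14 days later), then Day 2 and Day 5 calls, then Visit 8 | None |
| Daily survey (5.7) | Yes, in the usual care arm | None |
| Study CGM | Yes, in the usual care arm | Removed at the visit |
| On-call study provider (5.7.4) | Yes, study still running | Provided only while the study runs |

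If the arms are separated, an iLet-first participant has no survey or study CGM during the gap, but AEs are still queried when the next arm starts.

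**Step 2. How many participants**

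Inputs: the trial is "in 40 adult participants (18-85 years of age) with type 1 diabetes" (5.1), 20 at each site. Assumption: 1:1 allocation to sequence.
- All participants: 40 × 0.5 = 20.
- PC (injection users): 20 × 0.5 = 10. Endocrinology (EN, pump users): 10.
- If randomisation were unrestricted, the central 95% range is 14 to 26 of 40 (Binomial(40, 0.5)), and 6 to 14 of 20 within PC (Binomial(20, 0.5)).

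**Step 3. Chance of seeing no event in PC**

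The formula is (1 − p)^n, where p is the risk of an event after switch-off that meets the AE definitions in 9.3.1. The documents give no such risk, so a range is shown.

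| Assumed p | n = 10 (as planned) | n = 20 (all queried) |
|---|---|---|
| 2% | 0.98^10 = 82% | 0.98^20 = 67% |
| 5% | 0.95^10 = 60% | 0.95^20 = 36% |
| 10% | 0.90^10 = 35% | 0.90^20 = 12% |

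**Step 4. What zero observed events would rule out**

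The exact (Clopper-Pearson) two-sided 95% upper limit for 0 of n is 1 − 0.025^(1/n).
- PC: 1 − 0.025^(1/10) = 31% with 10 observed, and 1 − 0.025^(1/20) = 17% with 20.
- Whole trial: 17% with 20 observed, and 1 − 0.025^(1/40) = 8.8% with 40.

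**The case against.** The strongest reply is that this is a 40-person feasibility study with descriptive safety summaries and no endpoint for switch-off events. The primary endpoint, based on mean CGM glucose over days 3-14, is untouched. At a 2% risk, a query of all 20 PC participants would still find nothing two times in three. The AE definitions are also narrow: hypoglycemia counts only with altered consciousness and active help from another person, and hyperglycemia only with DKA or evaluation or treatment at a health care facility. A phone query under those definitions would not record milder excursions. All of this stands. It limits the importance of the point but does not remove the difference between sequences.

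A reader might also infer more than the documents support:
- **That nothing is collected after Visit 8.** The treatment-emergent definition has no end date, and 9.3.1 defines AEs by timing relative to participation, so a spontaneous report could still be recorded. The referral to the usual provider concerns usual diabetes care and does not redirect AE reports. What is missing is a scheduled query.
- **That the plan gives a 48-hour risk window for switch-off.** The sentence "The new equilibrium will not be reached until all the long-acting insulin has completely cleared their system, which may take 48 hours or more" describes injection users starting the iLet. The documents give no window for the reverse change.
- **That all 20 affected participants follow a study dosing schedule.** It applies only to injection users, about 10 in PC. EN participants return to their own pump therapy.
- **That the trial would make a misleading claim of no switch-off events.** The plan commits to no such statement.

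**Conclusion.** The point holds as a gap in scheduled safety capture. After the same study procedure, iLet-first participants have further AE queries and usual care-then-iLet participants have none. About 20 of 40 are affected, about 10 of them PC injection users. This rests on an assumed 1:1 sequence ratio; unrestricted randomisation would give 14 to 26. In PC, following all 20 instead of about 10 would lower the chance of missing every event from 82%, 60% and 35% to 67%, 36% and 12% at assumed risks of 2%, 5% and 10%. Those risks are illustrative and refer to events meeting the protocol's AE definitions.

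The primary and secondary glycemic endpoints are unaffected, and spontaneous reports remain possible. This is a cheap improvement, not a flaw that threatens the trial's main result.

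**What to change.** - In 5.6.1.4, 5.6.2.4 and the visit schedule, add one phone AE query a few days after Visit 8, comparable to the existing early follow-up calls, for participants coming off the iLet at that visit.
- Apply the same query after any early iLet discontinuation. Section 5.7.2 currently sends those participants back to their pre-study method without a scheduled contact. Section 9.2 uses data from those who withdraw only up to withdrawal, so state how the call applies to them.
- State that AE collection ends at that call for these participants, and at Visit 8 for those finishing in usual care.
- Include the events in the descriptive safety summary in 6.7.1.

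The cost is about 20 short calls by existing staff, one schedule line, and participation that ends a few days later for about half of participants. If the call were paid at the $20 mid-period rate in section 10, the total would be 20 × $20 = $400. The call is for data collection; no dosing instruction or clinical rule changes.
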